3 STUDY ALGORITHM

General Guidelines:

- Younger mini-cohorts will open when the mini-cohort (6) from the previous older cohort passes the safety (≤ 28 day data) & Day 7-12 PK evaluation (see Section 3.3)

4 STUDY OBJECTIVES

Primary Objectives:

1. To evaluate the pharmacokinetics of etravirine in combination with an OBR in HIV-infected children aged ≥ 2 months to < 6 years
2. To determine the safety and tolerability of etravirine in combination with an OBR through 48 weeks of therapy.
3. To determine the appropriate dose of etravirine in combination with an OBR for children aged ≥ 2 months to < 6 years.

Secondary Objectives:

1. To assess the antiretroviral activity of ETR containing regimens through 48 weeks of therapy.
2. To determine the immunological changes (change in CD4 percent and absolute count; CD4/CD8 ratio and percent) through 48 weeks of ETR therapy in combination with an OBR.
3. To determine changes in viral drug resistance during 48 weeks of ETR therapy in combination with an OBR.
4. To assess the relationship between ETR pharmacokinetics and the antiviral activity and safety of ETR containing regimens.\
5. To explore the relationship between subject-specific gene CYP profile, sex, age, weight, race, HIV regimen (e.g., boosted PI) and HIV response markers and pharmacokinetics of ETR.

5 ENDPOINTS AND OUTCOME MEASURES

Primary Endpoints:

Toxicity Endpoints:

- Termination from treatment due to a suspected adverse drug reaction (SADR)
- Adverse events of Grade 3 or higher severity
- Death

Pharmacokinetic Endpoint:

- Failure to meet PK targets (specified in Section 9.0)

Secondary Endpoints:

- Adverse events of Grade 3 or higher severity judged to be at least possibly attributable to the study medications
- Confirmed failure to suppress plasma HIV-1 RNA to ≤ 400 copies
- AND
- Failure to achieve at least a 2 log reduction (from baseline) in HIV-1 RNA at weeks 24 and/or 48 (confirmed in 1 to 4 weeks)
- Treatment discontinued due to toxicity or virologic failure
- Change in optimized background regimen due to virologic failure
- New onset OI or AIDS diagnosis
- Decline in absolute CD4 percent of $> 5\%$ any time after 12 weeks of therapy

Primary Response Variables:

- Pharmacokinetic parameters - AUC12h

Secondary Response Variables:

- Plasma HIV-1 RNA (copies/mL)
- CD4 counts and percent
- CD4/CD8 ratio and percent
- Genotypic and phenotypic measures of resistance at virologic failure and at early discontinuation
- Pharmacokinetic parameters - C12h and Cmax

Exploratory Response Variables:

- Patient-specific CYP gene profiles.

6 STATISTICAL METHODS AND RESULTS

6.1 Administrative Data: Accrual and Baseline Demographics

- Frequency tables on accrual in aggregate and broken down by cohort
- Reasons/frequencies for treatment discontinuation in aggregate and broken down by cohort
- Deaths (if any): Frequency, list of patients and complete etiologies
- Baseline Demographics: provides descriptive statistics for some of the variables of interest such as: gender, race and/or ethnicity, weight, age, RNA and CD4 (count and percentage) in aggregate and broken down by cohort

6.2 Safety

- Summary of Dose Finding Data (Through Week 4 – the point up to which the safety criteria are applied)

Descriptive statistics summarizing the safety data during the dose finding phase of the study. The safety data will be broken down by cohort and will present the results of the safety evaluations applied to each starting dose tested within each cohort, including information indicating which starting doses have passed or failed the safety guidelines. For each starting dose within each cohort, every adverse event of grade 3 or higher will be listed, along with patient demographics, the dose prescribed to the patient at the time of the event and the protocol team's assessment of the probability that this event was due to the study treatment.

- Analysis of Data Representing Exposure to the Doses Judged to be Optimal for Each Cohort

Primary Analysis of Safety: consists of data from “evaluable” patients only, performed on data through the weeks 24 and 48 visit at the final dose.

Each patient's safety data will be summarized as: the worst grade of adverse event experienced while on the first 24 and 48 weeks on the optimal dose of the study treatment and the worst grade of adverse event judged to be at least possibly due to study treatment during this time

period. Frequency distributions of these safety outcomes will be presented in the aggregate and broken down by cohort. Listings of all Grade 3+ events will be provided, broken down by type of toxicity (hepatic, hematologic, etc.).

The proportions of subjects experiencing grade 3+ adverse events will be presented in aggregate and broken down by Cohort, with these proportions bounded by exact 95% confidence intervals. Similar analyses will present the proportions of subjects exhibiting grade 3+ events which have been judged to be at least possibly related to study medication, again bounded by exact 95% confidence intervals.

NOTE: Given that the small sample sizes within cohorts will provide limited power for statistical tests of differences across age cohorts, interpretation of the results will depend upon whether differences across cohorts are great enough to be considered to be clinically significant. If no such differences are observed, then the clearest interpretation of the findings will come from the aggregated data, where analyses will have the greatest statistical precision. However, if results vary across cohorts to a clinically important extent, interpretation of results should take into account the issues represented by the stratification factor.

Key Secondary Safety Analysis

Safety assessments will be performed on long term data collected until the final patient reaches 5 years of follow-up. The key analyses will be similar to the Weeks 24 and 48 analyses described above, which will be performed on the data for all subjects through 5 years of follow-up.

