Skin events were the most frequently reported events of interest. ‘Rash cases’, referring to a grouped term combining all rash-related AEs except events considered ‘severe cutaneous reactions’, were reported in 6 (14.6%) children and 17 (28.3%) adolescents. Consistent with other drug-related rashes, rashes with ETR occurred early during treatment, with a median time to first onset of 10 days; were self-limiting, with a median duration of 7 days; and were usually grade 1 or 2 in severity. One subject in each age group developed a grade 3 rash. Four subjects (1 child and 3 adolescents) discontinued treatment because of rash. No grade 4 rashes or rash related SAEs were reported. Other relevant skin events of interest included 1 case of erythema multiforme (grouped under severe cutaneous reactions) and 1 case each of hypersensitivity and urticaria papular (grouped under angioedema). The incidence of neuropsychiatric events of interest, pancreatic events, lipid-related events and neoplasms was low ($\leq 2\%$). There were no hepatic, cardiac and bleeding events of interest reported in this study.

A slightly higher frequency of rash was observed in the PIANO study compared to the DUET studies in adults and therefore, a multivariate analysis was performed on the pooled data of the Week 48 data of the DUET studies and the Week 24 data of the PIANO study to investigate risk factors for developing rash when treated with ETR. The results of this analysis consistently showed that being female, but not age or participation in the PIANO study (a partial surrogate for age), is a risk factor for developing rash. No other risk factors could be firmly identified. This is also seen in the Week 48 PIANO data: Rash \geq grade 2 was reported in 13/64 (20.3%) of females vs 2/37 (5.4%) of males; discontinuations due to rash were reported in 4/64 (6.3%) of females vs 0/37 (0%) of males. Most often, rash was mild to moderate, of macular/papular type, and occurred in the second week of therapy. Rash was mostly self-limiting and generally resolved within 1 week on continued therapy.

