8.6 Analyses

8.61 Summary of Dose Finding Data

The analysis of dose finding data will consist of descriptive statistics summarizing the safety and PK data from the dose finding phase of the study. (See Section 9.0 for PK analysis). The safety data will be analyzed by cohort and will present the results of the safety evaluations applied to each starting dose regimen tested within each cohort, including information indicating which starting doses have passed or failed the safety guidelines. For each starting dose within each cohort, every adverse event of Grade 3 or higher will be listed, along with subject demographics, the dose prescribed to the patient at the time of the event and the protocol team's assessment of the probability that this event was due to the study treatment (not related, probably not related, possibly related, probably related or definitely related).

8.62 Analysis of Data Representing Exposure to the Doses Judged to be Optimal for Each Cohort

These analyses will be stratified by cohort. The findings will be presented in both in aggregate and broken down by cohort, with estimates bounded by 95% confidence limits. Given that the small sample sizes within cohorts will provide limited power for statistical tests of differences across age cohorts, interpretation of the results will depend upon whether differences across cohorts are great enough to be considered to be clinically significant. If no such differences are observed, then the clearest interpretation of the findings will come from the aggregated data, where analyses will have the greatest statistical precision. However, if results vary across cohorts to a clinically important extent, interpretation of results should take into account the issues represented by the stratification factor.

8.63 Primary Analyses - performed on data through the Week 24 and Week 48 visit

8.631 Safety

The primary safety analysis will include only subjects whose total exposure to ETR has been at the dose judged to be optimal for their cohorts. Subjects whose doses have been adjusted for inadequate PK will be excluded. Subjects who have been removed from treatment or have had their doses reduced due to toxicities while on the optimal dose will be included and treated as safety failures in the primary safety

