analysis. Additional analyses will look at the combined data from subjects whose doses failed and those who have been treated solely at the optimal doses determined for their cohorts and without individual PK determined dose adjustments. Sensitivity analyses will be performed to determine whether the exclusion of subjects whose doses have been adjusted creates a selection bias which impacts upon any results.

Each subject's safety data will be summarized as: the worst grade of adverse event experienced during the first 24 weeks (and 48 weeks) of exposure to the optimal dose of the study treatment and the worst grade of adverse event judged to be at least possibly related to study treatment during this time period. Frequency distributions of these safety outcomes will be presented in the aggregate and broken down by age. Listings of all Grade 3+ events will be provided, broken down by type of toxicity (hepatic, hematologic etc.).

The proportions of subjects experiencing Grade 3+ adverse events will be presented in aggregate and broken down by age cohort, with these proportions bounded by exact 95% confidence intervals. Similar analyses will present the proportions of subjects exhibiting Grade 3+ events which have been judged to be at least possibly related to study medication, again bounded by exact 95% confidence intervals.

8.632 Key Secondary Analyses

8.6321 Viral Load

Virologic outcomes, based on HIV-1 RNA (copies/ml), will be assessed at weeks 8, 12, 24 and 48. The criteria for success are: at least a 0.5 log₁₀ reduction in HIV-1 RNA (copies/ml) at week 8, at least a 1 log₁₀ reduction in HIV-1 RNA (copies/ml) at week 12 and either HIV-1 RNA ≤ 400 copies/ml or at least a 2 log reduction in HIV-1 RNA at weeks 24 and 48.

For regulatory submissions, at each of these time points the primary definition of virologic outcome will be calculated according to a Missing, Switch or Discontinuation = Failure (MSDF) algorithm – as codified by the FDA's snapshot algorithm. Subjects may be classified as virologic failures if they have missing HIV-1 RNA data throughout the window surrounding the time point of interest. (This window and related details will be defined in the analysis plan.) In addition subjects will be classified as virologic failures at any of these time points if they meet any of the following conditions prior to that time point:

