2 STUDY DESIGN

This is a Phase I/II, multicenter, open label 48 week pharmacokinetic, safety, tolerability and antiviral study of etravirine in combination with at least 2 active ARVs, including a boosted PI and NRTIs for treatment experienced HIV-1-infected infants and children ≥ 2 months to < 6 years cohorts.

The study will, in a sequential manner, accrue subjects for an initial dose finding intensive PK component for age related cohorts. It is expected that approximately 50 subjects will be accrued, to yield a minimum of 36 evaluable subjects (a minimum of 12 subjects in each cohort). Up to 18 subjects may be enrolled into Cohort I. The total sample size will depend upon the number needed to complete the dose finding stage of the study and the number of subjects required for regulatory approval of etravirine in these populations.

Evaluable will be defined as having been treated exclusively on the dose determined to be optimal for a given age cohort and having either completed 24 (or 48) weeks of exposure to the study drug or having been classified as a safety failure, due to a study drug related adverse event occurring during the first 24 (or 48) weeks of treatment.

The P1090 core protocol team will be responsible for reviewing the PK and safety data and approving the dose selection for each full and mini-cohort. The P1090 core protocol team will consist of the protocol chair and co-chairs, clinical trials specialist, NIAID and NICHD Medical Officers, data manager, pharmacologists, pharmacist, statisticians and Janssen representatives.

This study is designed to determine the appropriate etravirine dose for HIV-1-infected infants and children and to evaluate the PK, safety and tolerability of etravirine in this population. Etravirine (ETR) will be administered as 25 mg scored tablets and/or 100 mg tablets swallowed as a whole or dispersed in an appropriate liquid vehicle (see Section 5.2). ETR will be started concurrently with an optimized background regimen (OBR), while OBR will be based on clinical status, treatment history, resistance data and availability of appropriate pediatric dosing and formulations.

Children will be stratified by age, as follows:

- Cohort I: ≥ 2 year to < 6 years who are treatment experienced*
- Cohort II: ≥ 1 year to < 2 years who are treatment experienced*
- Cohort III: ≥ 2 months to < 1 year who are treatment experienced*, †

[figure not shown]

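### The evaluable definition, read as written, excludes children dose-reduced for toxicity whom Protocol 8.631 counts as safety failures, and termination for a SADR has no estimate in the primary safety analysis

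*SAP*

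**What the plan says.** **Who is in the primary safety set.** Protocol 8.631 opens by limiting the analysis to children whose whole ETR exposure was at the optimal dose. It then treats two kinds of dose change differently. For PK-driven changes: "Subjects whose doses have been adjusted for inadequate PK will be excluded". For toxicity, the rule covers children taken off the drug and also those who "have had their doses reduced due to toxicities while on the optimal dose will be included and treated as safety failures". That sentence sets no grade threshold. The same section adds a check: "Sensitivity analyses will be performed to determine whether the exclusion of subjects whose doses have been adjusted creates a selection bias".

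SAP 6.2 restricts the primary safety analysis to evaluable patients. The definition in SAP 2 reads: "having been treated exclusively on the dose determined to be optimal for a given age cohort and having either completed 24 (or 48) weeks". The alternative to completion is classification as a safety failure for a drug-related event. Protocol 3.0 and 8.1 use the same definition.

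**What is estimated.** Protocol 8.21 and SAP 5 list three primary toxicity endpoints. The first is "Termination from treatment due to a suspected adverse drug reaction (SADR"), again with no grade threshold; the others are Grade 3+ events and death. Protocol 8.631 says "The proportions of subjects experiencing Grade 3+ adverse events will be presented in aggregate and broken down by age cohort", using exact 95% intervals, and adds related Grade 3+ events. SAP 6.2 carries over those two proportions; for the first it says: "The proportions of subjects experiencing grade 3+ adverse events will be presented in aggregate and broken down by Cohort". It also gives frequency distributions of worst grade and worst related grade. SAP 6.1 tabulates reasons for discontinuation and lists deaths as administrative data, without intervals.

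**The concern.** There are two gaps. The first is in the analysis set. A child whose dose is cut for toxicity has not been treated exclusively on the optimal dose, so the evaluable definition removes that child. Protocol 8.631 says to keep the child and count a failure. The SAP carries only the definition, so a programmer working from it would exclude the child.

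The second is in the outcome. A child stopped for a Grade 1 or 2 SADR can enter the evaluable set as a safety failure and is then a non-event in both proportions that carry intervals. That child appears in the worst-grade distribution, which does not show who stopped, and in the discontinuation table, which is not restricted to the evaluable set.

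Safety and tolerability through 48 weeks is a primary objective. SAP 1 says the document covers the outcome measures for the primary manuscript and for ClinicalTrials.gov, so an endpoint with no estimator in it has no planned primary estimate.

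**Working it through.** **1. The plan's own figure.** Protocol Table 7 gives 4 of 36 as 11%, with exact 95% limits of 3% to 26%. The Clopper-Pearson limits for x of n are the 2.5% quantile of Beta(x, n − x + 1) and the 97.5% quantile of Beta(x + 1, n − x). For x = 4, n = 36 they are 3.1% and 26.1%. Table 7 is reproduced.

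**2. How each child is handled.**

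| Child on the optimal dose | Protocol 8.631 | Evaluable definition and SAP 6.2 |
|---|---|---|
| Stopped for a Grade 3+ SADR | In, safety failure | In, event in both proportions |
| Stopped for a Grade 1–2 SADR | In, safety failure | In, non-event in both proportions |
| Dose-reduced for toxicity | In, safety failure | Out: not treated exclusively on that dose |
| Dose-adjusted for inadequate PK | Out, with sensitivity analysis | Out, no sensitivity analysis |

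(The Grade 1–2 row assumes no separate Grade 3+ event.) The documents part at the second and third rows, and on the sensitivity analysis in the fourth.

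**3. Worth of one uncounted stop.** In the proportion of safety failures, one child is 1/36 = 2.8 points in aggregate and 1/12 = 8.3 points in a cohort. The missing row would read:
- 1 of 36: 2.8% (0.1% to 14.5%)
- 2 of 36: 5.6% (0.7% to 18.7%)
- 3 of 36: 8.3% (1.8% to 22.5%)
- 1 of 12: 8.3% (0.2% to 38.5%)

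**4. Effect of excluding one dose-reduced child.** Assume 4 Grade 3+ children among 36.
- If the excluded child is one of the four: 3/35 = 8.6% (1.8% to 23.1%), down from 11.1%.
- If that child had only lower-grade toxicity: 4/35 = 11.4% (3.2% to 26.7%), slightly up.

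The direction for the Grade 3+ proportion therefore depends on the grade of the excluded child. The safety-failure count loses that child either way.

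**5. How many low-grade stops to expect.** The documents give no figure for this trial. In the 6–17 year trial (PIANO, Protocol 1.32), "Four subjects (1 child and 3 adolescents) discontinued treatment because of rash". One subject in each age group had Grade 3 rash and nobody had Grade 4.
- Adolescents: at least 3 − 1 = 2 stops at Grade 2 or lower.
- Children: at least 1 − 1 = 0.

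The overall minimum is 2/101 = 2.0%. At that rate the chance of at least one such stop among 36 is 1 − (99/101)^36 = 51%. At the children's minimum of zero it is 0%. Both rates are lower bounds and cover rash only.

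AE stops of any grade, related or not, were 2/41 in children and 8/101 overall. Those rates give 2/41 × 36 = 1.8 and 8/101 × 36 = 2.9 stops among 36. They overstate low-grade SADR stops to the extent that they include Grade 3+ or unrelated events.

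**The case against.** Much of this is not of the SAP's making. The two Grade 3+ proportions and the *exclusively* wording are the protocol's own, and the conflict over dose reduction exists inside the protocol, between the definition in 3.0 and 8.1 and the sentence in 8.631. That stands, and it is why the fix covers both documents.

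A reader might infer that the SAP abandons the safety-failure idea and counts a child stopped for a mild reaction as event-free. The documents do not support that. SAP 2 keeps safety failure as a route into the evaluable set, low-grade reactions appear in both worst-grade distributions, and stops appear in the discontinuation table. The child is a non-event only in proportions defined at Grade 3+.

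A reader might also infer that the plan is bound to make ETR look better tolerated, for instance by setting 4/36 (11%) against 6/36 (17%) after adding two low-grade stops. Those counts are assumed, and the two figures measure different things. Step 4 shows that the Grade 3+ proportion can move either way.

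Few children may be affected. Protocol 6.12 continues drug at Grades 1 and 2, 6.13 allows continuation or temporary interruption for Grade 1–2 rash, and the toxicity criteria in 6.8 start at Grade 3 apart from the high-AUC route. The individual dose-reduction route is in 9.34 and needs both an AUC12h above 4380 ng·h/mL and poor tolerance. Protocol 8.1 also plans secondary analyses of all safety data, including children with adjusted doses, and SAP 6.2 plans long-term analyses of all subjects. These limit the size. They do not remove the conflict over the primary set, and the long-term analyses, planned to be similar, add no SADR-termination estimate.

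**Conclusion.** The point holds as a conflict between a stated inclusion rule and the definition that implements it, plus a listed primary endpoint with no estimate in the primary safety set. It should be fixed before the analysis is run.

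The size is 2.8 points per uncounted child at N = 36 and 8.3 points in a cohort of 12, against intervals that are already wide. The number of such children is unknown and probably small. The only guide is PIANO, where both inferred low-grade rash stops were in adolescents and the minimum in children is zero.

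The dose-reduction part rests on reading *exclusively* literally. It could be read as yielding to the more specific sentence in 8.631, but the SAP does not contain that sentence.

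**What to change.** 1. In Protocol 3.0 and 8.1 and in SAP 2, reconcile the evaluable definition with 8.631: children stopped or dose-reduced for toxicity while on the optimal dose stay in the primary safety set as safety failures, despite the *exclusively* condition. The opening sentence of 8.631 should carry the same exception.
2. Restore the 8.631 rule and its selection-bias sensitivity analysis in SAP 6.2.
3. In SAP 6.2, add three proportions with exact 95% intervals, in aggregate and by cohort: terminated for a SADR of any grade; died; safety failure as 8.631 defines it (removed or dose-reduced for toxicity). A wider composite that also includes Grade 3+ events is optional.
4. The sponsor must reconcile the tolerability wording in Protocol 9.34. The rule for AUC12h above 4380 ng·h/mL describes a dose that is not well tolerated, but its parenthesis says there is no toxicity of Grade 3 or above. Until that is settled, the grade at which a dose-reduced child would be classified is unclear.

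The cost is wording in two documents, three table rows and one sensitivity analysis, all from data already collected. The safety summary may look slightly less favourable.

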3.7 Early Discontinuation

Subjects who are withdrawn from study drug within the first 48 weeks of study will not enter long term follow-up but will be followed for safety for 4 weeks, as per Appendix ID. Additionally, any AEs will be followed until satisfactory clinical resolution (i.e. value returns back to subjects baseline value) or stabilization (to be agreed upon with the sponsor). All grade 3 and grade 4 laboratory abnormalities as well as any laboratory abnormalities resulting in an increase of 2 DAIDS Grades from baseline, will be followed until they return to baseline or within 1 Grade from baseline.

4.0 **SELECTION AND ENROLLMENT OF SUBJECTS**

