5.5 Long Term Safety Follow-up

Provided that the overall data for this drug appear to be generally favorable, each subject who successfully completes 48 weeks of ETR treatment will continue to receive study drug through the study, and be followed on study for long-term safety follow-up (see Appendix IE) for up to 5 years or until any one or more of the following events occur within the 5 years:

- The age-appropriate formulations provided by the study are available locally from another source; OR
- The subject is no longer deriving benefit; OR
- The subject meets a protocol-defined reason for discontinuation; OR
- Pharmaceutical development of ETR for that age cohort is terminated

Subjects in countries where ETR, darunavir 100 mg/mL suspension, darunavir 75 mg tablets, and darunavir 150 mg tablets continue to be unavailable locally at the end of the planned 5 year long- term safety follow-up program will be provided the drug either through a P1090 protocol amendment or through other sources, such as another Janssen R&D-sponsored program, government programs, and aid and assistance programs. It is also expected that such programs will be in place in all countries where study sites are located within the planned 5 year duration of long-term safety follow-up phase.

Once subjects enter the Long Term Safety Follow-up phase, they will be seen in clinic every 12 weeks for safety visits and laboratory evaluations until one of the above criteria are fulfilled, as per Appendix IE. Sites should record any laboratory results, diagnoses etc. that are recorded as part of standard of care as well as perform the study mandated HIV-1 RNA assay (See Appendix IE).

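### The SAP carries the Week 24/48 crude proportion to 5-year safety data without saying how unequal follow-up or the denominator will be handled

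*SAP*

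**What the plan says.** **Method.** Under Key Secondary Safety Analysis, SAP section 6.2 says of the long-term data: "The key analyses will be similar to the Weeks 24 and 48 analyses described above". The same sentence says they cover all subjects through 5 years. The Week 24 and 48 analyses summarise each child by worst grade and report the proportions with any Grade 3+ event and with a related Grade 3+ event, "with these proportions bounded by exact 95% confidence intervals". They are restricted to evaluable children. SAP section 2 defines these as children treated only at the optimal dose who completed the period or were safety failures through a drug-related event.

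**Length of follow-up.** Protocol section 5.5 keeps a child who completes 48 weeks "for up to 5 years or until any one or more of the following events occur within the 5 years". The listed events are:
- "The age-appropriate formulations provided by the study are available locally from another source"
- "The subject is no longer deriving benefit"
- "The subject meets a protocol-defined reason for discontinuation"
- an end to development of the drug for that age cohort.

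The section also expects other supply programmes in every site country within the 5 years. Protocol section 3.7 says children withdrawn from study drug before Week 48 "will not enter long term follow-up but will be followed for safety for 4 weeks", with longer follow-up only for unresolved events and laboratory abnormalities. SAP section 1 puts the last long-term visit at Week 288.

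**What is absent.** Protocol section 8.1 adds secondary analyses of all safety data to the end of the study but names no method that allows for time at risk. Neither document plans a person-time rate, a time-to-event estimate or a rule for early exit in the safety analysis.

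**The concern.** At Weeks 24 and 48 the evaluable rule makes the period nearly the same for every child counted, so a binomial proportion has a clear meaning. Over 5 years it does not. A child released soon after Week 48 because the drug became available locally and a child observed to Week 288 each add one to the denominator, with very different chances of showing an event. The exact interval reflects only sampling error in the count, not the unobserved time.

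Two things are at stake. First, adverse event tables are to be updated publicly after Week 288, and a reader may take the proportion for a 5-year risk. Second, SAP section 6.2 has cohort differences judged by clinical significance, without formal tests. Exit depends on country, response and age-cohort-specific development, so differing exit times may create or hide a difference between cohorts.

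**Working it through.** **1. The plan's own estimator.** Protocol Table 7 gives exact 95% limits for the proportion with Grade 3+ events. Clopper-Pearson limits reproduce all 12 rows to rounding. For example, 4/36 gives 3.1% to 26.1% (stated 3% to 26%), and 9/36 gives 12.1% to 42.2% (stated 12% to 42%). The intervals are correct for a period observed in full. The documents state no 5-year figure.

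**2. Direction.** With all subjects in the denominator, the children with an observed event are a subset of those who would show one under full follow-up. The proportion can therefore only equal or fall below the proportion under full follow-up. This needs no assumption about why children leave.

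**3. Illustrative size, all-subjects denominator.**
- From the documents: exits after Week 48 (a = 48/52.18 = 0.920 years); last visit Week 288 (T = 288/52.18 = 5.519 years).
- Assumed: true risk p to Week 288; constant hazard h = −ln(1 − p)/T; a share f reaches Week 288; the rest exit uniformly between a and T, independently of risk.
- Average risk observed in a leaver: q = 1 − [exp(−ha) − exp(−hT)] / [h(T − a)].
- Expected crude proportion: f·p + (1 − f)·q.

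For p = 33%: h = 0.4005/5.519 = 0.0726 per year, and q = 1 − (0.935 − 0.670)/0.334 = 0.205. With f = 50%, the crude proportion is 0.5 × 0.33 + 0.5 × 0.205 = 26.7%.

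| True risk to Week 288 | f = 75% | f = 50% | f = 25% |
|---|---|---|---|
| 25% | 22.6% | 20.1% | 17.7% |
| 33% | 29.9% | 26.7% | 23.6% |
| 50% | 45.6% | 41.2% | 36.7% |

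The shortfall runs from 2.4 points (25 − 22.6) to 13.3 points (50 − 36.7). If half the children instead leave right at Week 48, the crude figure is 14.8% for a true 25% and 19.7% for a true 33%.

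**4. Front-loaded risk.** For a true 33% and f = 50%, the crude figure is 29.4%, 31.6% or 33.0% when 50%, 80% or 100% of the cumulative hazard falls before Week 48. At 80% the gap is 1.4 points.

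**5. If the evaluable rule is carried over.** Event-free early leavers drop out, so the proportion becomes [f·p + (1 − f)·q] / [f + (1 − f)·q]. For p = 33% this gives 37%, 44% and 59% at f = 75%, 50% and 25%; at f = 50% it is 0.267/0.602. This treats every Grade 3+ event as keeping the child in the set. The SAP keeps early leavers only for drug-related failures, so the overstatement would be smaller where leavers' events were unrelated.

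**6. Does a time-to-event estimate help?** In simulation (N = 36, 4,000 runs per scenario, exits as in step 3), Kaplan-Meier averaged 24.9–25.2%, 32.9–33.1% and 49.7–50.0% for true risks of 25%, 33% and 50%. It is noisier: at 33% and f = 50% its standard deviation is 9.0 points against 7.3 for the crude proportion. These exits are unrelated to risk, so the result does not cover informative exit.

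**The case against.** The strongest reply is that the SAP never calls this result a 5-year risk. A proportion with a Grade 3+ event during available follow-up is a legitimate descriptive incidence in a single-arm study, provided exposure is shown. That stands, and it is why the crude figure can be kept. But the SAP plans no exposure summary to go with it.

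Some of what is needed already exists. SAP section 6.1 tabulates reasons for treatment discontinuation by cohort, and all Grade 3+ events are listed. Neither gives time at risk.

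The documents do not support four stronger readings that a reader might infer:
- **Understatement is certain.** The direction depends on the denominator. The all-subjects wording favours understatement, but the reference back to analyses of evaluable children is not reconciled with it.
- **The gap is large.** At an assumed hazard of 0.10 per child-year, risk to Week 288 is 1 − exp(−0.10 × 5.52) = 42%, against 1 − exp(−0.10 × 2) = 18% if every child were followed for 2 years. Neither the hazard nor the follow-up comes from the documents. Constant hazard also fits poorly for rash, the main treatment-limiting event: Protocol section 1.32 reports a median onset of 10 days in the trial in children aged 6 to 17.
- **Later-opened cohorts will look safer.** No document dates local availability by cohort, and the 5 years are counted per child. Differing exits may distort comparisons either way.
- **An early leaver is recorded as five event-free years.** The SAP does not say so. That child is counted as having no event observed.

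**Conclusion.** The point holds as a gap in the long-term analysis: follow-up is unequal by design, the denominator is ambiguous, and no planned method allows for time at risk. As literally written, with all subjects counted, the proportion equals or understates Grade 3+ risk to Week 288. Under the evaluable rule the error tends the other way. Opposite directions under two plausible readings are themselves a reason to amend.

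Only the direction for a given denominator follows from the documents. The 2 to 13 points rest on constant hazard, uniform exits after Week 48 that are unrelated to risk, 25% to 75% of children reaching Week 288, and true risks of 25% to 50%. Mostly early risk brings the gap close to nil; a cluster of exits at Week 48 widens it at a given risk and share leaving. This is a secondary analysis. The primary Week 24 and 48 safety results and dose selection, which uses safety data to Week 4, are not affected.

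**What to change.** In SAP section 6.2, for data beyond Week 48:

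1. State that the denominator is all treated children.
2. Keep the crude proportion only as a descriptive on-study incidence, shown with child-years of observation in total and by cohort.
3. Add the rate of first Grade 3+ event and of first related Grade 3+ event per 100 child-years, with exact Poisson intervals. Counting first events avoids intervals that are too narrow because of repeat events in one child.
4. Add cumulative incidence of the first event from first dose, with numbers at risk by year and cohort.
5. Use one risk window for items 3 and 4: time on etravirine plus the protocol's post-treatment safety period. The SAP should name that period, since Protocol Appendix ID has a visit 4 weeks after stopping and Appendix IE has one 14 days after therapy.
6. Tabulate ends of follow-up by the Protocol section 5.5 reasons, by cohort.
7. Add a sensitivity analysis for exits through loss of benefit or toxicity, for example counting them as events at exit. These exits may be informative, and censoring alone would not remove that bias.

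The Week 24 and 48 proportions stay as they are. The cost is a few SAP sentences and two or three extra tables from dates already collected at the 12-weekly visits. The new estimates will be less precise, and the reported long-term risk may be higher than the crude proportion.
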